Definition of indicators: CR or PR after the end of treatment is considered objective remission, prostate cancer has no biochemical recurrence at the end of the last treatment, and no regional lymph nodes or distant metastasis are considered objective remission. Proportion of participants who experienced objective remission at each time point after the end of the last treatment.

Metric type: Qualitative.

Data collection time: screen period, 3 days, 1 month \pm 7 days, 2 months, \pm 7 days, 3 months, \pm 7 days after the end of the last treatment.

Evaluation time: 3 days, 1 month \pm 7 days, 2 months, \pm 7 days, 3 months, \pm 7 days after the last treatment.

Site of evaluation: Tumor receiving radiation therapy.

Evaluation method: The changes in tumor CT or MRI imaging before and after treatment were evaluated by an independent imaging review panel according to RECIST 1.1. At 3 months of radiographic evaluation, if PD is found, PET-CT is required to confirm it.

Calculation formula: ORR = number of subjects in objective response / total number of subjects \times 100%.

Criteria: See RECIST 1.1 for details. At the time of 3-month imaging evaluation, if the patient is found to have PD, PET-CT examination is required to confirm it, if progress is confirmed, it is recorded as PD, if progress cannot be confirmed, it may be false progression, and it is recorded as SD. If prostate cancer does not have biochemical recurrence, PET-CT examination is not required, and there is no metastasis by default, which is regarded as objective remission, and if biochemical recurrence occurs, it is regarded as not objectively remission, and PET-CT is required to confirm tumor metastasis.

Note: Participants who aborted the trial for any reason (other than loss to follow-up) before the end of the last radiotherapy were considered to have not responded objectively. Disease site evaluation uses the same approach as baseline, including consistent contrasted/non-contrast scans and prompt scanning. If changes are needed, the case must be discussed with a radiologist to determine whether an alternative approach is possible. If not, the objective situation in the future is unclear.

(2) Tumor disease control rate (DCR).

Reason for selection: DCR 3 months after the end of the last treatment was the primary evaluation index, and DCR at other follow-up time was used as a secondary evaluation index.

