Definition of indicators: the occurrence of CR, PR and SD after the end of treatment is disease control; No biochemical recurrence at the end of prostate cancer treatment, no regional lymph nodes or distant metastases, considered disease control. Proportion of participants who developed disease control at one month after the end of the last treatment.

Metric type: Qualitative.

Data collection time: screen period, 3 days , 1 month \pm 7 days, 2 month \pm 7 days after the end of the last treatment.

Evaluation time: 3 days, 1 month \pm 7 days, 2 month \pm 7 days after the last treatment.

Site of evaluation: Tumor receiving radiation therapy.

Evaluation method: The changes in tumor CT or MRI imaging before and after treatment were evaluated by an independent imaging review panel according to RECIST 1.1. At 3 months of radiographic evaluation, if PD is found, PET-CT is required to confirm it.

Calculation formula: $DCR = \frac{\text{number of disease control subjects}}{\text{total number of subjects}} \times 100\%$.

Criteria: See RECIST 1.1 for details. At the time of 3-month imaging evaluation, if the patient is found to have PD, PET-CT examination is required to confirm it, if progress is confirmed, it is recorded as PD, if progress cannot be confirmed, it may be false progression, and it is recorded as SD. If prostate cancer does not have biochemical recurrence, PET-CT examination is not required, and there is no metastasis by default, which is regarded as tumor control, and if biochemical recurrence occurs, it is regarded as tumor not controlled, and PET-CT is required to confirm tumor metastasis.

Note: Participants who aborted the trial for any reason (other than loss to follow-up) before the end of the last radiotherapy were considered to have PD or was uncontrolled. Disease site evaluation uses the same approach as baseline, including consistent contrasted/non-contrast scans and prompt scanning. If changes are needed, the case must be discussed with a radiologist to determine whether an alternative approach is possible. If not, the objective situation in the future is unclear.

(3) Tumor markers (if needed)

Reason for selection: The Guidelines for the Review of Clinical Evaluation Technologies of Proton Carbon Ion Therapy System (CFDA Circular No. 4, 2018) suggests that changes in tumor markers and functional imaging parameters should be used as reference factors for effectiveness evaluation.

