- (3) The missing values of DCR and primary safety evaluation indicators (proportion of CTCAE grade 3 toxicities, proportion of CTCAE grade 4 and 5 toxicities) at 3 months after the end of treatment can be estimated using worst-case scenarios.
- (4) The missing values of qualitative secondary effectiveness evaluation indicators ORR, DCR and long-term follow-up effectiveness evaluation indicators can be estimated using worst-case scenarios;
- (5) The missing values of quantitative secondary efficacy evaluation indicators DOR, tumor markers, product ease assessment and long-term follow-up effectiveness evaluation indicators were not estimated.
- (6) Erroneous, unreasonable data (out-of-range data and data that contradicts other data or indicators of the study protocol) can be treated as missing values;
- (7) Worst-case estimates are used for missing values for all minor safety indicators;

- (8) The sensitivity analysis of the main effectiveness evaluation indicators and main safety evaluation indicators after treatment was carried out in the whole analysis center.
- (9) The sensitivity analysis of all secondary effectiveness evaluation indicators after treatment was carried out in the whole analysis center.
- (10) For all secondary safety evaluation indicators after treatment, sensitivity analysis was carried out in the security dataset.

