DCR	Disease Control Rate	Tumor disease control rate
ECOG	Eastern Cooperative Oncology Group	Eastern Oncology Collaborative Group
FAS	Full Analysis Set	Full analysis set
ICH	The International Council for Harmonisation of Technical Requirement for Pharmaceuticals for Human Use	International Harmonization Council for Technical Requirements for Pharmaceuticals for Human Use
MedDRA	Medical Dictionary for Regulatory Activities	Medical Dictionary of Regulatory Activities
NYHA	New York Heart Association	New York Heart Society
ORR	Objective Response Rate	Objective response rate
PD	Progressive Disease	Disease progression
PET	Positron Emission Tomography	Positron emission tomography
PN	Preferred Name	Preferred name
PPS	Per-Protocol Set	Conforms to the scenario set
PR	Partial Response	Partial relief
PSA	Prostate Specific Antigen	Prostate-specific antigens
PT	Preferred Terms	Preferred term
SAE	Serious Adverse Events	Serious adverse events
SAP	Statistical Analysis Plan	Statistical analysis plan
SAS	Statistical Analysis System	Statistical analysis system
SD	Stable Disease	Stable disease
SLD	Sum of Longest Diameter	Sum of longest diameters of tumors
SOC	System Organ Class	Systematic organ classification
SS	Safety Set	Security datasets
TEAE	Treatment Emergent Adverse Event	Adverse events during the treatment period
TNM	Tumor, Node, Metastasis	Tumors, lymph nodes, metastases
WHODD	World Health Organization Drug Dictionary	World Health Organization Dictionary of Medicines
WOCF	Worst Observation Carried Forward	Worst observed data carryover

This statistical analysis plan (SAP) refers to the E9 guiding principles of the International Council for Harmonization of Technical Requirements for Pharmaceuticals for Human Use (ICH) Guidance for Industry: Statistical Principles for Clinical Trials ICH E3 Guidance for Industry: Structure and Content of Clinical Study Reports Relevant national regulations and guidelines, according to the clinical study protocol titled "Varian ProBeam360 Proton Therapy System China Clinical Trial (Wuhan)" (version number: V1.0, Version Date: 2024-01-12) developed.

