2.1.2 Secondary effectiveness measures

- **Objective response rate (ORR)**

CR or PR was considered objective remission at the end of treatment, no biochemical recurrence occurred at the end of prostate cancer at the end of treatment, and no regional lymph node metastasis or distant metastasis was considered objective remission. Proportion of subjects with objective remission at each time point after the end of the last treatment.

Calculation formula: $ORR = \text{number of subjects with objective remission} / \text{total number of subjects} \times 100\%$

- **Tumor disease control rate (DCR) at 1 month after the end of last treatment**

The occurrence of CR, PR and SD after the end of treatment was considered to be disease control, and the absence of biochemical recurrence at the end of treatment of prostate cancer was considered to be disease control. Proportion of subjects with disease control 1 month after the end of the last treatment.

Calculation formula: $DCR = \text{number of subjects under disease control} / \text{total number of subjects} \times$

100%

- **Tumor markers (if required)**

Tumor marker examination was performed and clinically significant changes in tumor markers (before and after radiation therapy) were reported at the discretion of the investigator.

- **Ease of use (ProBeam System, Radiation Therapy Management Software (Aria), Radiation Therapy Planning Software (Eclipse))**

Investigators using the corresponding functions scored according to the Likert scale and collected open-ended questions to evaluate the comprehensive feeling of ease of use during the treatment.

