4.3 Effectiveness indicators are missing

When analyzing the main effectiveness evaluation indicators based on PPS, it is not necessary to consider filling them.

In the sensitivity analysis of the main effectiveness evaluation indicators based on FAS, the missing values of the main effectiveness evaluation indicators were not filled.

The missing values of qualitative secondary effectiveness evaluation indicators ORR and DCR were filled by the method of worst observational data carryover (WOCF).

The missing value of the quantitative secondary effectiveness evaluation index DOR was not filled.

Other secondary effectiveness evaluation indicators, such as tumor markers, tumor-specific symptoms, and product ease of use, were not filled.

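### For a missing early DCR the protocol names worst case but the SAP uses WOCF, which counts a missing 1-month result as controlled whenever the 3-day reading shows control

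*Protocol*

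**What the plan says.** **Missing-data rule.** Protocol 4.7.2 item (4) reads: "The missing values of qualitative secondary effectiveness evaluation indicators ORR, DCR and long-term follow-up effectiveness evaluation indicators can be estimated using worst-case scenarios". SAP 4.3 covers the same endpoints differently: "The missing values of qualitative secondary effectiveness evaluation indicators ORR and DCR were filled by the method of worst observational data carryover (WOCF". The SAP abbreviation list expands WOCF as "Worst Observation Carried Forward".

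**Schedule and definition.** Protocol 3.1.4.2 (2) sets the early DCR readings: "Evaluation time: 3 days, 1 month" and 2 months after the last treatment. CR, PR and SD all count as control. The SAP names months 1 and 2 in its secondary purpose (1.1.2) but only month 1 in 2.1.2 and 5.4.2.

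**Subjects who abort before the end of radiotherapy.** Unless they are lost to follow-up, the protocol Notes assign them an outcome. For ORR they "before the end of the last radiotherapy were considered to have not responded objectively"; for secondary DCR they "before the end of the last radiotherapy were considered to have PD or was uncontrolled". SAP 2.1.2 defines both rates over the total number of subjects but does not repeat either Note.

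**The concern.** The two documents give different instructions for the same missing values. For early DCR the instructions can point in opposite directions. Worst case treats a missing reading as a failure. WOCF copies an earlier reading, and for month 1 that reading was taken only 3 days after the last fraction. Any result short of progression at 3 days then stands in for control at 1 month.

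The SAP text is likely to decide what is reported, because Protocol 4.8 normally limits the trial report to analyses agreed in the SAP. The more conservative rule named in the protocol would then not be the one applied. At stake is the reported secondary DCR, and to a lesser degree ORR.

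**Working it through.** **1. The plan's own numbers.** With a 95% expected rate, an 80% target, two-sided 0.05 and 80% power, the normal approximation gives n = (1.960 × √(0.8 × 0.2) + 0.842 × √(0.95 × 0.05))² / 0.15² = 41.59, so 42. Then 42/0.9 = 46.7, so 47. The plan's figures reproduce and are not in dispute. They supply N = 47 and 47 − 42 = 5 expected dropouts.

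**2. What each rule does when month 1 is missing.** The 3-day reading is the only earlier scheduled post-treatment reading. SAP 4.1 provides for unscheduled data in WOCF only for the main effectiveness indicator.

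| 3-day reading | DCR, worst case | DCR, WOCF | ORR, worst case | ORR, WOCF |
|---|---|---|---|---|
| CR or PR | not controlled | controlled | non-response | response |
| SD | not controlled | controlled | non-response | non-response |
| PD | not controlled | not controlled | non-response | non-response |
| none | not controlled | nothing to carry | non-response | nothing to carry |

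For DCR the rules differ after a 3-day CR, PR or SD. For ORR they differ only when every earlier reading is a response. That includes prostate cancer without biochemical recurrence, which Protocol 3.1.4.2 (1) counts as objective remission. At month 2, WOCF takes the worse of the 3-day and 1-month readings.

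**3. Size of the difference.** Let x be the number controlled among those scanned at month 1. Let k be the number who miss month 1 after a 3-day reading of control. The denominator is all N = 47, following the formula in SAP 2.1.2.

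- Worst case: x/N
- WOCF: (x + k)/N
- Difference: k/N

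The counts below are assumptions, not figures from the documents. Intervals are Clopper-Pearson 95%.

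- **Main illustration:** 42 scanned and 41 controlled; k = 3 after a 3-day SD; 2 stopped during radiotherapy. Worst case is 41/47 = 87.2% (74.3–95.2). WOCF is 44/47 = 93.6% (82.5–98.7). Difference 3/47 = 6.4 points.
- **One missing scan:** 46 scanned and 44 controlled; k = 1. Worst case is 44/47 = 93.6%; WOCF is 45/47 = 95.7%. Difference 1/47 = 2.1 points.
- **All 5 expected dropouts with a 3-day reading of control:** 42 scanned and 40 controlled; k = 5. Worst case is 40/47 = 85.1% (71.7–93.8). WOCF is 45/47 = 95.7% (85.5–99.5). Difference 5/47 = 10.6 points.

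**4. Subjects with no post-treatment scan.** FAS entry (SAP section 3) needs one treatment and any post-baseline observation, so a subject without a post-treatment scan can be in the set. If that subject aborted before the end of radiotherapy, the protocol Notes assign a failure. If lost to follow-up before the first scan, the Notes do not apply and WOCF has nothing to carry. Only a worst-case rule covers that subject.

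**The case against.** **The protocol rule is soft.** Item (4) is permissive (*can be*), worst case is not defined, and 4.7.2 presents its items as basic principles to be finalised at data review. Protocol 4.1 leaves detailed methods to the SAP. In a translated text, WOCF may simply be how the SAP puts worst case into practice. This has weight: the SAP is not plainly in breach of a binding rule. But it confirms that the rule needs stating, and if WOCF was intended, the effect on 1-month DCR remains.

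**WOCF is not always favourable.** A 3-day PD is carried as PD. The documents give no figure for how often SD is seen at 3 days, so the illustrations are conditional on that reading.

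**Stronger readings that the documents do not support.**

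- A reader might infer that ORR is equally distorted, for example when a subject has SD at 3 days, PR at months 1 and 2, and no month-3 scan. WOCF and worst case both make that subject a non-responder.
- A reader might infer that subjects who stop during radiotherapy are left out, and might enlarge the gap by removing them from the denominator. The protocol Notes score most of them as failures, the SAP does not revoke the Notes, and SAP 2.1.2 divides by the total number of subjects. What stands is that the SAP text on its own does not cover them.
- SAP 4.3 also says: "When analyzing the main effectiveness evaluation indicators based on PPS, it is not necessary to consider filling them". A reader might infer that month-3 ORR and DCR in the PPS have different denominators. That depends on how the PPS criterion is read. If the required primary assessment is the month-3 reading, the mismatch disappears.

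**Conclusion.** The point holds for early DCR. The two documents name different rules, and WOCF turns a missing 1-month reading into control whenever the 3-day reading is CR, PR or SD. The difference is k/47: about 6 points in the main illustration, about 2 with one missing scan, and about 11 at most if all 5 expected dropouts had a 3-day reading of control. These sizes rest on assumed counts and on keeping all 47 in the denominator.

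For ORR the two rules seldom differ. The omitted Notes are a gap in the SAP's wording; the remaining hole is subjects lost to follow-up before any post-treatment scan.

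Importance is modest. ORR and early DCR have no target value and do not enter the pass/fail criteria in Protocol 4.5. Only the reported secondary rates are affected.

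**What to change.** - **SAP 4.3:** replace WOCF for secondary DCR and ORR with the worst-case rule. A missing reading counts as not controlled or not responded, with all subjects of the analysis set in the denominator. This also covers subjects lost before any post-treatment scan. Show observed cases as support.
- **SAP 2.1.2:** restore the protocol Notes on subjects who abort before the end of radiotherapy, for both ORR and DCR.
- **Protocol 4.7.2 item (4):** change *can be* to *are*.

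The cost is a few lines of text and a small programming change before database lock. The downside for the sponsor is a slightly less favourable secondary DCR.

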4.7.1 Data statistical methods

Statistical analysis with SAS 9.4 software.

All data are described statistically, including demographics, baselines, all efficacy measures, and all safety data. The measurement data give the mean, standard deviation, minimum, maximum, median, 25th quantile and 75th quantile; The counting data gives the frequency and the corresponding percentage.

Effectiveness Analysis:

The number and percentage of cases achieving DCR were calculated, and the Clopper-Pearson method was used to calculate the 95% confidence interval for tumor disease control rate. ORR was calculated and the Clopper-Pearson method was used to calculate the objective response rate 95% confidence interval. Descriptive statistics on the percentage change from baseline of the sum of the longest diameter (SLD) of the measurable tumor. The Waterfall Chart was made by the maximum percentage reduction in SLD per patient compared to the screening period.

The *Kaplan-Meier* method was used to calculate the median duration of response, median progression-free survival, median survival, and overall survival, and plotted *K-M* curves (long-term follow-up data).

For tumor markers, compare and evaluate the changes before and after treatment, and give clinical evaluation [no clinical significance, clinically significant (tend to normal), clinically significant (tend to be abnormal), not checked].

Safety Analysis:

Descriptive statistics were used to classify organ systems in MedDRA medical terms, and the incidence, occurrence, and severity of adverse events, adverse reactions, and serious adverse events were summarized.

Laboratory indicators, ECOG physical status classification and other safety-related indicators were compared and evaluated before and after treatment, and clinical evaluation ([no clinical significance, clinically significant (tending to normal), clinically significant (tending to abnormal), not checked], CTCAE grade evaluation before and after treatment cross-table.

4.7.2 Missing, unused, or erroneous data (including mid-exit and evacuation) and unreasonable data

All missing, unused or erroneous data (including mid-exit and withdrawal) and unreasonable data will be discussed and finalized by investigators and

biostatisticians during the blinding review phase. The basic statistical principles of these data processing are as follows:

- (1) Describe the details of each shedding case;
- (2) Missing data from baseline, which can not be estimated;

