4.4 Handling of missing safety indicators

The missing values of safety evaluation indicators were filled by the method of Worst Observational Data Carryover (WOCF).

According to the conservative principle, if the severity of an AE is missing, it will be recorded as "grade 3" in the summary description, and if the relationship between an AE and the investigational medical device is missing, it will be recorded as "probable" in the summary description as "probable".

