5.5 Safety evaluation index

The safety metrics are based on the Safety Dataset (SS).

The main safety indicators included the proportion of CTCAE grade 3 toxicity and the proportion of CTCAE grade 4 and 5 toxicity.

Secondary safety measures included the proportion of CTCAE grade 1 and 2 toxicity, laboratory tests, ECOG performance status classification, tumor recurrence rate, adverse events, serious adverse events, and device defects.

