5.5.2 Laboratory tests

The results of laboratory indicators (blood routine, coagulation routine, urine routine, blood biochemistry) and their changes from baseline were summarized and described at each planned visit, the changes before and after treatment were evaluated, and the pre- and post-treatment cross-over tables of clinical evaluation (normal, abnormal and clinically significant) were given.

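### Protocol 4.7.2(7) and SAP 4.4 give different fill rules for missing secondary safety values, and neither is confined to a sensitivity analysis

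*Protocol*

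**What the plan says.** **Protocol.** Section 4.7.2 item (7) reads "Worst-case estimates are used for missing values for all minor safety indicators". Minor here means secondary. Section 3.1.5.2 lists these indicators as grade 1-2 toxicity, laboratory tests, ECOG status, AE rate, SAE rate and device defects. Item (7) is worded as a requirement, whereas items (3) and (4), on the primary indicators and on ORR and DCR, only permit a worst-case estimate. Item (10) adds a sensitivity analysis of the secondary safety indicators in the safety set (SS) but does not say what differs in it. For before/after comparisons of laboratory, ECOG and other safety indicators, section 4.7.1 ends its list of categories with "clinically significant (tending to abnormal), not checked".

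**SAP.** Section 4.4 reads "The missing values of safety evaluation indicators were filled by the method of Worst Observational Data Carryover (WOCF"). The abbreviation list expands WOCF as "Worst Observation Carried Forward". Section 4.4 also covers incomplete AE records: "According to the conservative principle, if the severity of an AE is missing, it will be recorded as" grade 3, and a missing relationship to the device is recorded as probable. Section 5.5 lists the secondary safety measures, including "ECOG performance status classification, tumor recurrence rate, adverse events, serious adverse events, and device defects". In section 5.5.2, laboratory results and "their changes from baseline were summarized and described at each planned visit"; the before/after cross-table described there has no not-checked category. Section 5.5.3 summarises ECOG by visit. Section 5.6 covers sensitivity analysis of the main effectiveness measure only.

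**The concern.** By-visit laboratory and ECOG tables should show the course after radiotherapy, including whether on-treatment abnormalities resolve. A filled value in such a table is not a measurement at that visit. It shifts the mean, the change from baseline and the shift table, and it hides how many subjects were not assessed.

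The two documents also prescribe different fills, so a programmer cannot follow both. Neither says what worst means for a parameter that can be too high or too low, or what a missing value is for an AE or SAE, where no record normally means no event. At stake is the accuracy of the descriptive safety tables in the report. The pass/fail criteria in protocol 4.5 use DCR, grade 3 toxicity and grade 4-5 toxicity, so the secondary tables do not decide the trial.

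**Working it through.** **The plan's own figure.** The sample size sets the scale. With a target of 80%, an expected rate of 95%, two-sided alpha 0.05 and power 80%:

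n = (1.960 × √(0.8 × 0.2) + 0.842 × √(0.95 × 0.05))² / 0.15² = 41.6, so 42; 42 / 0.90 = 46.7, so 47.

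Both figures reproduce. The gap, 47 − 42 = 5, is used below only as the top of an assumed range. Protocol 4.4 defines the 10% as subjects who cannot enter the primary analysis, which is not a rate of missing safety data.

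**The two rules by type of table.**

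| Table | Protocol worst case | SAP WOCF |
|---|---|---|
| AE or SAE incidence (ever occurred) | Literal reading: a missing subject counts as an event | No change; an event never recorded cannot be carried forward |
| Worst grade per subject over the trial | Could be raised | No change |
| Laboratory and ECOG by visit | An undefined worst value is entered | The subject's earlier worst value is entered |

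**Incidence under a literal worst case.** Assume an SS of 47 and m subjects with a missing outcome and no recorded event. The increase is m/47:

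- m = 1: 1/47 = 2.1 points
- m = 2: 2/47 = 4.3 points
- m = 3: 3/47 = 6.4 points
- m = 5: 5/47 = 10.6 points

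With no event observed and m = 5, the table would show 10.6% instead of 0%. With 2 recorded events it would show 7/47 = 14.9% instead of 2/47 = 4.3%. Under WOCF the increase is zero in every case.

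**By-visit proportion under WOCF (assumed inputs).** Let p be the proportion abnormal at month 3 among 42 measured subjects, and q the proportion of the 5 unmeasured subjects with an earlier abnormal value. The filled figure is (42p + 5q)/47:

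- p = 10%, q = 20%: (4.2 + 1)/47 = 11.1%
- p = 10%, q = 60%: (4.2 + 3)/47 = 15.3%
- p = 10%, worst case: (4.2 + 5)/47 = 19.6%
- p = 20%, q = 20%: (8.4 + 1)/47 = 20.0%, no shift

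The shift is 5(q − p)/47. It is upward when abnormality was more frequent earlier than at month 3, which is the pattern of recovery.

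**By-visit mean under WOCF (assumed inputs, direction only).** Blood counts are the only laboratory tests repeated weekly on treatment (protocol 3.1.5.2), so take a white count: baseline 6.0, treatment low 3.5, month 3 value 5.5, five subjects unmeasured at month 3. The filled mean is (42 × 5.5 + 5 × 3.5)/47 = 5.29. The change from baseline becomes −0.71 instead of −0.50. All of these values are invented, so this shows the direction of the shift, not its size.

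**Internal consistency.**

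- Protocol 4.7.1 keeps not checked as a reporting category; a complete fill would leave it empty.
- Protocol 4.7.2(5) and SAP 4.3 leave missing tumor markers unfilled, whereas missing laboratory values are filled. No reason is given.
- Protocol 4.7.2(6) lets erroneous data be treated as missing; item (7) would then turn them into worst-case values.
- SAP 4.1 says that unscheduled data feed WOCF for the main effectiveness measure but does not say whether they do for safety.

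**The case against.** The strongest reply is that the SAP governs. Protocol 4.1 refers methods to the SAP, and 4.8 normally admits only SAP content to the report. The SAP rule repeats a value observed in the same subject and creates no AE or SAE. This stands. A reader might infer that the main safety tables would report toxicity that nobody observed; for WOCF that is not supported, because the toxicity was seen, only at another visit.

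A reader might also infer that every subject with incomplete follow-up becomes an SAE case. Neither document says so. The SAE rate is built from events the investigator recorded, and absence of a record is not called a missing value. The 2.1 to 10.6 points therefore depend on a literal reading of item (7) that the SAP does not carry forward.

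It can also be said that the documents do not plainly state that the filled tables are the main ones. Protocol 4.7.1 has its not-checked category, item (10) mentions a sensitivity analysis, and SAP 4.1 limits by-visit safety summaries to scheduled test results. This stands in part: the reading is an inference. It is a strong one, because SAP 4.4 fills without restriction, SAP 5.6 has no secondary-safety sensitivity analysis, and no separate table of observed values is specified. Under protocol 4.8, such a table added later would be exploratory.

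The fill is also defended as conservative, since it runs against the device. A conservative view can instead be given from real data, by the worst observed value. Leaving the matter to the data review described in protocol 4.7.2 is weak in an open-label single-group trial, where results may already be known.

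Finally, the first sentence of SAP 4.4 also reaches the primary safety indicators, where one subject matters more: 2/47 = 4.3% is within the 5% limit and 3/47 = 6.4% is not. That is correct, but it is a separate question from the secondary tables.

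**Conclusion.** The concern holds in a limited form. Two stated rules conflict with each other and with the protocol's not-checked category, and neither defines worst for a laboratory value that can be abnormal in either direction. As the SAP is written, by-visit laboratory and ECOG summaries would contain values not measured at that visit and would tend to understate recovery. AE and SAE incidence is unaffected under the SAP rule.

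The only route to counting unrecorded events is the protocol's worst case read literally, which adds 2.1 to 10.6 percentage points for an assumed 1 to 5 of 47 subjects. The number missing is an assumption throughout, and the laboratory example shows direction only. The effect is on descriptive tables, runs against the device and does not touch the pass/fail rule. It should still be corrected, because it is a stated rule that would bias the reported results and it is cheap to change.

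**What to change.** Reconcile protocol 4.7.2(7) and the first sentence of SAP 4.4 so that both state the following for secondary safety:

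- Laboratory and ECOG results are summarised by visit on observed values, with n and the number not checked. SAP 5.5.2 takes up the not-checked category from protocol 4.7.1.
- AE, SAE and grade 1-2 incidence is the number of subjects with recorded events over SS.
- Each laboratory parameter and ECOG gets one added row for the worst observed post-baseline value, with the direction of worst stated. For parameters abnormal both ways, give the lowest and the highest.
- Any worst-case or WOCF fill appears only as a labelled sensitivity analysis under item (10), with the rule defined and the use of unscheduled data stated.

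The SAP 4.4 rules for missing AE severity and relationship can stay, since they concern events already recorded. The rewording should say explicitly which rule still applies to the primary safety indicators, so that they are not changed by accident.

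The cost is wording in two documents and about one extra row per parameter. The tables will no longer be complete at every visit.
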